5.4.2. Physician Questionnaire

Product ease of use will be evaluated using on the Investigator Questionnaire (Appendix E) at the end of subject's study participation.

TABLE 5.1 TIME AND EVENTS SCHEDULE

REQUIRED ASSESSMENTS	SCREENING VISIT Day 0 (May be combined with first interim visit, Day 1)	INITIAL VISIT Day 1	INTERIM VISITS Approx. Every 7 Days	FINAL VISIT ⁵ Approx. 28 days after Day 1 visit
Informed Consent	X			
Demographics	X			
Medical History	X			
Concomitant Medication	X			
Physical Examination	X			
Doppler Assessment	X ^{1,3}			
Blood Glucose Assessment	X ^{1,2,4}			
Wound Screening Evaluation	X			
Confirmation of Eligibility	X	X	X	
Adverse Event Assessment	X	X	X	X
Wound Evaluation		X	X	X
Wound Photograph		X	X	X
TheraHoney® Foam Flex		X	X	
Secondary Dressing Notation		X ¹	X ¹	
Mechanical debridement noted		X ¹	X ¹	
Investigator Questionnaire				X

¹If required

²Within 30 days of screening visit or at screening visit

³Within 90 days of screening visit or at screening visit

⁴Diabetic subjects only

⁵Final visit may be an interim visit in the event patient heals fully before 4 weeks and no longer requires treatment

6. CLINICAL SUPPLIES AND PRODUCT AVAILABILITY

Medline Industries, Inc. will provide the Investigators with supplies of TheraHoney® Foam Flex dressings and Optifoam® Gentle Super Absorbent silicone dressings (to be used as a secondary dressing if required) for the duration of the study.

Storage conditions for these materials will be maintained in accordance with the guidelines set forth in the product labeling. A record of the study-related materials supplied by the Sponsor, Medline Industries Inc., will be maintained by the Investigators at both clinic locations. Dispensing of these supplies will also be noted.

All unused investigation product will be disposed of properly by the investigational site, in accordance with their standard destruction procedures.

Medline Industries, Inc. will provide the eKare inSight® wound assessment camera, the ultrasonic pocket Doppler (SONOTRAX Basic), and glucose monitor (EVENCARE G3) for the period of the study. This equipment is to be stored securely throughout the study and will be returned to Medline Industries, Inc. upon completion of the study.

7. ADVERSE EVENTS

All Adverse Events (AE) are defined as set forth in the International Conference on Harmonization (ICH) Guideline for Clinical Safety Data Management: Definitions and Standards for expedited Reporting E2A (R1) and the Food and Drug Administration Code of Federal Regulations Title 21, part 812, as appropriate.

AEs will be collected throughout the study and documented in the subject's medical record and on the appropriate AE form.

All events will be followed until the event has been resolved or, in the case of permanent impairment, until the event stabilizes.

Information regarding any AEs occurring during the study will be recorded on the appropriate AE form. Such information will include, at a minimum, the date of the event, severity, outcome, and the relation (if any) to the investigational product.

7.1. Adverse Event Reporting

Beginning at enrollment and proceeding throughout the duration of the follow-up period, the PI will closely monitor each subject for the development of adverse events.

An AE is any new untoward medical occurrence (sign, symptom, or laboratory finding) in a clinical investigation subject, who was administered an Investigational Product that does not necessarily have a causal relationship with the Investigational Product.

The severity of all adverse events will be graded on a scale of one through five according to the most recent version of the Common Terminology Criteria for Adverse Events

guideline, where each grade represents a unique clinical description based on this general guideline:

- **Grade 1:** Mild; asymptomatic or mild symptoms; clinical or diagnostic observation only; intervention not indicated.
- **Grade 2:** Moderate; minimal, local or noninvasive intervention indicated; limited age-appropriate instrumental activities of daily living.
- **Grade 3:** Severe or medically significant but not immediately life-threatening; hospitalization or prolongation of hospitalization indicated; disabling; limiting activities of daily living involving self-care.
- **Grade 4:** Life threatening consequences; urgent intervention indicated
- **Grade 5:** Death related to AE

The PI will categorize the relationship of the event to the Investigational Product as follows:

- **Unrelated:** This category applies to those adverse events which, after careful consideration, are clearly and incontrovertibly due to extraneous causes (disease, environment, etc.)
- **Possible:** This category applies to those adverse events for which, after careful medical consideration at the time they are evaluated, a connection with the Investigational Product administration appears unlikely but cannot be ruled out with certainty.
- **Probable:** This category applies to those adverse events which, after careful medical consideration at the time they are evaluated, are felt with a high degree of certainty to be related to the Investigational Product.
- **Definite:** This category applies to those adverse events which, after careful consideration, are clearly and incontrovertibly due to the Investigational Product.

Any AE will be documented on the AE Report Form (Appendix F).

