5.3.5. TheraHoney® Foam Flex Application

The application of TheraHoney® Foam Flex will be performed according to the product labeling during the Initial Visit (Day 1) and subsequent Interim Visits. Dressing changes will take place daily, with the Investigator instructing participants on how to change the dressing at home on days when they do not visit the clinic. The use of secondary dressings will also be done at the discretion of an Investigator. At the discretion of an Investigator, use of TheraHoney® Foam Flex should be discontinued due to adverse events or lack of wound closure response.

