7.2. Serious Adverse Event Reporting

Beginning at enrollment and proceeding throughout the duration of the follow-up period, the PI will closely monitor each subject for the development of serious adverse events (SAEs).

An SAE is defined as any adverse experience that results in any of the following outcomes:

- Fatal
- Life-threatening
- Requires or prolongs inpatient hospitalization

- Results in persistent or significant disability or incapacity
- A congenital anomaly or birth defect
- An important medical event or requires medical intervention to prevent one of the above outcomes

Any SAE occurrences (whether or not considered to be related to the Investigation Product) must be reported immediately, within 48 hours of awareness to Medline Industries, Inc. on the SAE Report Form (Appendix G) and be documented on the AE Report Form (Appendix F).

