8.3.2. Secondary Endpoints

- Percent patients with 100% wound closure in each group
- Number of new infections in wound site
- Change in wound volume over time, measured similarly to percent necrotic tissue; analyzed by providing the 95% confidence interval for the mean
- Mean odor score between groups; analyzed by providing the 95% confidence interval for the mean
- Mean pain score between groups; analyzed by providing the 95% confidence interval for the mean
- Mean BWAT score between groups; analyzed by providing the 95% confidence interval for the mea

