8.4 ANALYSIS OF SAFETY DATA

Subject withdrawal and the incidence and nature of AEs will be summarized in safety data assessments. All treated subjects, defined as the safety population, will be the basis for all safety analyses.

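### Sections 7 and 7.1 give two unreconciled definitions of an adverse event, and read literally 7.1 lets non-serious worsening of the existing wound or pain go unrecorded

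*Combined protocol and SAP*

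**What the plan says.** Two definitions of an AE stand side by side. Section 7 opens with "All Adverse Events (AE) are defined as set forth in the International Conference on Harmonization (ICH) Guideline for Clinical Safety Data Management" and adds a federal device regulation, to be applied where appropriate. The text of these sources is not reproduced. Section 7.1, the only definition written out for the site, reads "An AE is any new untoward medical occurrence (sign, symptom, or laboratory finding) in a clinical investigation subject", and requires every AE to go on the Appendix F form. Section 7.2 is worded differently: "An SAE is defined as any adverse experience that results in any of the following outcomes". It does not require the event to be new.

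Section 8.4 sets the safety output, in all treated subjects: "Subject withdrawal and the incidence and nature of AEs will be summarized in safety data assessments". Section 5.3.5 names two separate grounds for stopping the product at the investigator's discretion: "use of TheraHoney® Foam Flex should be discontinued due to adverse events or lack of wound closure response".

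Among the efficacy outputs, 8.3.1 uses the mean reduction in necrotic tissue. Section 8.3.2 uses means for wound volume ("Change in wound volume over time, measured similarly to percent necrotic tissue; analyzed by providing the 95% confidence interval for the mean"), pain ("Mean pain score between groups; analyzed by providing the 95% confidence interval for the mean"), odor and the BWAT. It also lists two endpoints that are not means: "Percent patients with 100% wound closure in each group", and a count of new wound-site infections. Under 8.3.3 the efficacy set requires a necrotic tissue value at Day 1 and at the Final Visit.

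**The concern.** Section 4.2.1 requires a wound at least 4 weeks old with at least 20% necrotic tissue. The condition in which harm from a dressing would show is therefore present in every subject before treatment. If a wound enlarges or becomes more necrotic, or existing pain increases, a site holding to the word *new* can regard it as a known condition and complete no AE form. Because 5.3.5 lists failure to respond apart from AEs, the same deterioration can also be handled as non-response only.

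Pain matters here because the labeling in Appendix A names a temporary increase in pain as a possible effect. In a subject who already has pain, that effect is a worsening.

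Safety is a stated objective (3.2) and there is no comparator. Events missed this way move the summary in one direction, toward fewer.

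**Working it through.** The plan states no figure on this point, and 8.2 sets 20 evaluable subjects without a power calculation, so there is nothing to reproduce. The check is first one of wording, then an illustration of scale.

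**1. Where each kind of worsening would appear**

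- Serious: reportable under 7.2, and also on Appendix F.
- Infection: documented, ends participation (5.3.1), counted (8.3.2).
- Leads to withdrawal: the withdrawal is summarized (8.4), but 8.4 does not ask for reasons.
- Non-serious, not infected, subject completes: no output counts it, unless the site reads 7.1 broadly or applies the external definition.
- Product stopped for non-response: need not appear as an AE.

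**2. Whether the means would show it**

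With n = 20, the t critical value on 19 df is 2.093, so the 95% CI half-width is 2.093 × SD / √20 = 0.468 SD. The changes below are assumed, not taken from the documents.

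- *Pain, as change from the Day 1 score.* 3 subjects rise by 4 points and 17 fall by 2. Mean = (3 × 4 − 17 × 2) / 20 = −1.10. SD = 6 × √(0.15 × 0.85 × 20/19) = 2.198. Half-width = 0.468 × 2.198 = 1.03. The CI is −2.13 to −0.07: apparent improvement with 15% worse.
- *Necrotic tissue score (1 to 5), each subject moving one category.* 5 worsen and 15 improve. Mean reduction = (15 − 5) / 20 = 0.50. SD = 2 × √(0.25 × 0.75 × 20/19) = 0.889. Half-width = 0.42. The CI is 0.08 to 0.92, so the criterion in 8.3.1 (lower bound above zero) is met with 25% worse. With 6 worse the CI is −0.04 to 0.84 and it fails.

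A subject who stops early without a Final Visit necrotic value is not in the efficacy set at all. Section 5.4 turns an interim visit into the Final Visit only when the wound has healed.

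**3. What a count would show**

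Exact (Clopper-Pearson) 95% intervals at n = 20:

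| Subjects | Percent | 95% CI |
|---|---|---|
| 0 | 0% | 0% to 16.8% |
| 1 | 5% | 0.1% to 24.9% |
| 3 | 15% | 3.2% to 37.9% |
| 5 | 25% | 8.7% to 49.1% |

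**4. Why a count needs a margin**

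Table 5.1 gives Day 1 plus about four follow-ups, so about five readings. For a stable wound with exchangeable continuous measurement noise (assumed), Day 1 is the highest of five with probability 1/5. The chance that some follow-up exceeds Day 1 is then 1 − 1/5 = 80% for one measure. Counting any rise would mostly count noise.

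Pain has a further limit. It is scored after the dressing is applied (5.3.1; Appendix D says within 10 minutes of the change), so the Day 1 score already includes any effect of the dressing and is not a pre-treatment baseline.

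**The case against.** The best defence is that 7.1 is silent on worsening rather than hostile to it. A deeper wound or stronger pain can be read as a new sign or symptom, and Section 7 brings in an external definition that may settle the matter. This stands in part. A reader might infer that the protocol excludes worsening from its AE concept; the documents do not support that, because the external text is not reproduced and neither definition is said to prevail. What remains is an ambiguity, with the narrower wording being the one the site has in front of it.

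A reader might also infer that the efficacy section reports only means and that no other output could reveal harm. That is wrong. Full closure and new infections are not means, 7.2 captures serious worsening, and withdrawals are summarized in all treated subjects. None of these, however, counts a wound or pain that worsens without being serious or infected in a subject who completes.

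Finally, the 0/20 against 3/20 contrast assumes its own conclusion: three worsenings, all unrecorded, and no other event. That is a fair criticism. The contrast shows what a gap of that size would do to the summary, not how likely it is. Nor do the documents establish that wound deterioration is the most likely harm of this product; the labeling names increased pain.

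**Conclusion.** The point holds in a limited form. Sections 7 and 7.1 are not reconciled. Followed literally, 7.1 allows non-serious, non-infected worsening of the target wound or of existing pain to go unrecorded as an AE, or to be handled only as non-response. The planned means, taken in the evaluable set, do not reliably reveal it. The direction of bias is clear (fewer events); its size is unknown, because the documents give neither a worsening rate nor a threshold for worsening. The intervals and mean changes above are illustrations at n = 20 under assumed changes. This does not undermine the study, but it should be corrected because the safety conclusion has no control arm to set it against.

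**What to change.** 1. In 7.1, insert *or worsened* after *new*, and say in Section 7 how that definition relates to the external sources so that one rule governs.
2. Add one sentence to 7.1: clinically relevant worsening of the target wound or of pain, as judged by the Investigator, is recorded on Appendix F.
3. Optionally, in 8.4, tabulate for all treated subjects the number and percent whose wound size or percent necrotic tissue worsens from Day 1 by more than a prespecified margin larger than measurement error, with an exact 95% CI.
4. Describe any pain change as change from the Day 1 post-application score, not from pre-treatment pain.

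The cost is a few sentences and at most one table. The Appendix D form already collects wound dimensions, percent necrotic tissue and pain at each visit; the only new work is choosing and justifying the margin. The reported AE rate may be somewhat higher. This is a recording and reporting change and leaves clinical management as it is.

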7.2. Serious Adverse Event Reporting

Beginning at enrollment and proceeding throughout the duration of the follow-up period, the PI will closely monitor each subject for the development of serious adverse events (SAEs).

An SAE is defined as any adverse experience that results in any of the following outcomes:

- Fatal
- Life-threatening
- Requires or prolongs inpatient hospitalization

- Results in persistent or significant disability or incapacity
- A congenital anomaly or birth defect
- An important medical event or requires medical intervention to prevent one of the above outcomes

Any SAE occurrences (whether or not considered to be related to the Investigation Product) must be reported immediately, within 48 hours of awareness to Medline Industries, Inc. on the SAE Report Form (Appendix G) and be documented on the AE Report Form (Appendix F).

7.3. Unanticipated Adverse Event Reporting

An unanticipated AE is defined as any AE caused by, or associated with, an Investigational Product whose nature or severity is not consistent with the applicable product information.

Reports which add significant information on specificity or severity of a known, already documented serious AE constitute unexpected events.

All serious unanticipated AE that occur throughout the study duration are to be reported to Medline Industries, Inc., as well as to the respective IRB, as soon as possible and no later than 48 hours following acknowledgement.

For questions regarding this process or the event, you may contact your Medline clinical designee or the Medline Clinical Associate Director:

Name: [name]
Office: [contact]
[contact]
E-mail: [contact]

8. DATA MONITORING AND STATISTICS

All information and data concerning subjects or their participation in this study will be considered confidential. Only authorized personnel will have access to these confidential files. All data used in the analysis and reporting of this evaluation will be without identifiable reference to the subject. No personal subject identification information should be included in any data submitted for the study.

8.1. DATA COLLECTION

All required data for this study will be collected on standardized CRFs (Appendix D). Qualified site personnel will perform primary data collection, drawn from the initial, interim, and final visits. Study monitors and/or designees will perform ongoing verification of source documentation via periodic on-site visits and remote monitoring. During this time, information will be reviewed for completeness and accuracy. Queries

may be generated for the site to resolve any issues identified. Data from the CRFs will be transferred to a secure electronic database maintained by Medline Industries, Inc. and stored on a secure server.

8.2. SAMPLE SIZE JUSTIFICATION

This is an observational study without a comparison group; therefore a formal power analysis is not feasible. Rather, the study will aim to collect data from 20 patients with evaluable data. The key analysis for the study is providing a quantitative estimate of debridement of necrotic tissue. To this end, a 95% confidence interval centered on the sample mean for necrotic tissue reduction will be created using the critical t value for this analysis; this will provide the best point estimate for debridement, as well as a measure of uncertainty, which will takes the sample size into account.

8.3. ANALYSIS OF EFFICACY DATA

8.3.1. Primary Endpoint

Percent reduction in necrotic tissue will serve as the primary endpoint. The Investigator will analyze wound photographs and visually inspect the wound in order to calculate percent necrotic tissue and enter a value of 1-5, corresponding to:

- 1 = No necrotic tissue
- 2 = 0% - 25%
- 3 = 26% - 50%
- 4 = 51% - 75%
- 5 = 76% - 100%

The 95% confidence interval for the mean reduction in necrotic tissue across the study period will be evaluated to determine if the lower bound is positive, which would be an indication of significant reduction in necrotic tissue.

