5.2.6. Wound Screening Evaluation

The type of wound will be diagnosed and receive a diagnostic code based on type of wound at initial presentation (e.g., venous, diabetic, pressure, etc.). A history of the wound will be collected to determine that it has been present for greater than four weeks, but less than 52 weeks. Further, every attempt should be made to document the types of dressings previously used in the treatment of the wound in question, up to six months prior to enrollment. An image of the wound will be taken with the eKare inSight® wound assessment camera, which will calculate wound size and tissue composition of the wound. The Investigator will analyze the wound and the image of the wound to confirm wound size and percent necrotic tissue in order to verify the wound meets the inclusion criteria stated above.

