5.3.2. Photographing the Wound

In order to obtain an accurate assessment of the wound, photographs of the wound and surrounding skin must be obtained using the eKare inSight® wound assessment camera. Photographs taken with the eKare device will include a visible label containing the following information subject number and date.

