10.4 APPENDIX D: Case Report Form

Case Report Form (R16-017)

Subject Number:	Visit Date:	Visit Time:	AM	PM	Visit Type and Number:	
Height (inches):	Weight (lbs):	Age:				
Sex:  Male	 Female					
Race:  White	 Black	 Hispanic or Latino	 Asian	 Other/Mixed Race	 Native American	
Was mechanical debridement used?  Yes		 No				
Was a secondary dressing used?  Yes		 No	If yes, what kind? _____			
Wound Assessment						
Physical Examination and Wound Zoom Analysis			Bates – Jensen Wound Assessment Tool (BWAT)			

Diagnosis: _____
 
What is the percent of necrotic tissue? _____ %
 
Wound size (cm): Width _____ x Length _____ x Depth _____
 
Evaluation of odor: _____
 
 1  2  3  4
 
VAS Pain scale score within 10 minutes following dressing change: _____
 
 0  1  2  3  4  5  6  7  8  9  10
 
Site Infection: Yes No
 
If yes, discontinue subject and note steps taken:
			
1. Skin: _____
 
2. Depth: _____
 
3. Edges: _____
 
4. Undermining: _____
 
5. Necrotic Tissue Type: _____
 
6. Necrotic Tissue Amount: _____
 
7. Exudate Type: _____
 
8. Exudate Amount: _____
 
9. Skin Color Surrounding Wound: _____
 
10. Peripheral Tissue Edema: _____
 
11. Peripheral Tissue Induration: _____
 
12. Granulation Tissue: _____
 
13. Epithelialization: _____
 
TOTAL BWAT SCORE: _____
			

Place photograph of the wound from the Wound Zoom camera below:

Subject #: _____ **Date:** _____

*Please note that the information in the picture should match the above information.

Signature _____ **Date** _____

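### The primary result rests on the unmasked treating Investigator's reading, and the plan has no separate analysis of the camera's own figure to test that dependence

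*Combined protocol and SAP*

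**What the plan says.** Section 8.3.1 defines the primary value: "The Investigator will analyze wound photographs and visually inspect the wound in order to calculate percent necrotic tissue", then a score from 1 to 5 is entered. Section 5.3.1 describes the same assessment as eKare photographs plus the Investigator's visual confirmation. The decision rule in 8.3.1 is that the 95% interval for the mean reduction "will be evaluated to determine if the lower bound is positive, which would be an indication of significant reduction in necrotic tissue". No minimum reduction is set.

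The study is open-label with a single group (4.1, 8.2), and the Investigators are the subjects' own physicians (2.3). Photographs "will include a visible label containing the following information subject number and date" (5.3.2), so the visit order is visible to the reader. No masked or independent reading and no check of reader agreement is described.

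On the camera, 5.2.6 says of the eKare device at screening that it is one "which will calculate wound size and tissue composition of the wound". Section 5.3.2 and Table 5.1 require wound photographs with this device at Day 1, the interim visits and the Final Visit. The CRF (Appendix D) asks "What is the percent of necrotic tissue" once, under a heading that joins physical examination with Wound Zoom analysis, and it calls the camera Wound Zoom rather than eKare inSight.

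**The concern.** In a before-and-after study without controls, nothing cancels a tendency to read wounds more favourably at the end than at the start. The rule asks only for a lower limit above zero, so a small shift in one direction can be enough to meet it. The person reading knows the product, the visit and the subject's course. What is at stake is whether a claim of significant reduction describes the wounds or partly the reader. The plan names a device said to quantify tissue composition, but the data as collected would not let anyone tell the two apart.

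**Working it through.** **Inputs**
- n = 20 evaluable subjects (8.2: "the study will aim to collect data from 20 patients with evaluable data"). There is no power or precision figure to reproduce; 8.2 says "a formal power analysis is not feasible".
- Interval: "a 95% confidence interval centered on the sample mean for necrotic tissue reduction will be created using the critical t value" (8.2), so t(0.975, 19) = 2.093.
- Success: lower limit above 0 (8.3.1).
- Assumption: the analysed quantity is the change in the 1-5 score, Day 1 minus Final.

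**Step 1: smallest shift that meets the rule.** Let u subjects be read one band better, d one band worse, and the rest be unchanged.
- Mean m = (u - d)/20
- s² = [(u + d) - 20m²]/19
- Lower limit = m - 2.093 × s/√20

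For u = 4, d = 0: m = 0.20, s² = (4 - 0.8)/19 = 0.1684, s = 0.410, half-width = 2.093 × 0.410/4.472 = 0.192. Lower limit **+0.008**: rule met.

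For u = 3, d = 0: m = 0.15, s² = (3 - 0.45)/19 = 0.1342, s = 0.366, half-width 0.171. Lower limit **-0.021**: rule not met.

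Four is the minimum and needs the other 16 subjects to show exactly zero change:

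| Subjects worse (d) | Fewest improvers (u) | Lower limit |
|---|---|---|
| 0 | 4 | +0.008 |
| 1 | 7 | +0.033 |
| 2 | 9 | +0.036 |
| 3 | 10 | +0.001 |
| 4 | 12 | +0.016 |

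**Step 2: chance of declaring success with no true change.** Assume that each subject independently has probability p of being read one band better and q of one band worse. Sum the trinomial probabilities over all (u, d) whose lower limit is above zero. The documents give no p or q, so a range is shown:

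| p (drop) / q (rise) | Success declared |
|---|---|
| 20% / 20% | 2.2% |
| 10% / 5% | 5.6% |
| 20% / 10% | 11.5% |
| 15% / 5% | 14.8% |
| 20% / 5% | 26.0% |
| 25% / 5% | 37.7% |

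The nominal value is 2.5%. Symmetric error does not inflate it; directional error does.

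**Step 3: dependence on the definition.** If percent reduction means each subject's relative change in score, four one-band shifts meet the rule for 21 of the 35 possible mixes of starting scores and narrowly fail for the other 14. The minimum of four is therefore not universal.

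**Step 4: can the device figure be separated from the reading?** Section 5.2.6 attributes a calculated tissue composition to the camera at screening. That the figure also exists at Day 1 and Final is an inference from the same camera being required then. The CRF has one percent field of unstated origin and a different camera name. As written, a separate device-based analysis is neither planned nor assured by the data collected.

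**The case against.** The strongest reply is that the reading is neither unsupported nor detached from the camera: 5.3.1 bases it on the device's photographs, images go on the CRF, and 8.1 provides for source verification. That stands. A reader might infer that the plan ignores the camera. It does not; the gap is that the only value analysed is the unmasked entry.

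Second, a reader might infer that the device percentage ought to replace the Investigator's. The documents do not support that. They give no accuracy or agreement data for the device's necrosis figure and do not say how much operator input it needs. The BWAT instructions in Appendix C also judge necrotic tissue type partly by consistency and adherence, which a photograph cannot assess directly. This stands, and it is why the fix asks for both values.

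Third, the inflation is not peculiar to a banded judgement. In the 25%/5% case the bias is 0.20 and the SD is √(0.30 - 0.04) = 0.51, a ratio of 0.39. A normally distributed measure with the same standardised bias would pass about as often (38%). So the percentages show how exposed this rule is to directional error without a control arm; they do not show that the device would do better.

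Fourth, the study is openly descriptive, and comparison with other therapies is outside its scope (2.4). That excuses the missing control arm. But 8.3.1 still attaches a significance claim to the lower limit, so the claim's dependence on the reader matters.

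**Conclusion.** The concern holds in limited form. The primary value is an unmasked treating Investigator's entry, the success rule has no margin and no control, and the plan offers no way to see whether the conclusion depends on that reading. Under the assumed error rates, false success runs from about 6% to 38% when the error favours improvement, and stays at 2.2% when it is symmetric.

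This rests on three assumptions: the change in the 1-5 score is what is analysed, the error rates are illustrative, and the device produces a tissue percentage at Day 1 and Final as it is said to do at screening. A reader might infer that the Investigators will in fact read optimistically, or that any four favourable readings would carry the study. Nothing in the documents shows the first, and the second fails as soon as one subject worsens.

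**What to change.** 1. Correct the camera name on the CRF so that it agrees with 5.2.6 and 5.3.2.
2. Split the CRF percent field in two, device-calculated percent necrotic tissue and Investigator's percent, both completed at Day 1 and Final, with the device value recorded before the Investigator's reading.
3. In 8.3.1, pre-specify the same 95% t interval on the device-calculated percent reduction, reported beside the Investigator-based result. Call a significant reduction robust only if both lower limits are positive.
4. The sponsor may make the device value primary if it is satisfied with the device's accuracy, which the documents do not give.

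The cost is one extra CRF field and some wording in 8.3.1, with no added visit or procedure, provided the camera reports tissue composition at these visits as it does at screening. The downside is that the device may misclassify some tissue; the paired values would show where the two readings part.
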